3.9.3.2. Electrocardiograms

Descriptive statistics for ECG parameters (heart rate, PR interval, RR interval, QRS interval, QT interval, and QTc interval) at baseline and change from baseline values at each assessment time point and at the end of the double-blind treatment period will be presented by treatment group for the double-blind period. QTc interval will be calculated using both Bazett

(QTcB = QT/(RR)^{1/2}) and Fridericia (QTcF = QT/(RR)^{1/3}) corrections; if RR is not available, it will be replaced with 60/HR in the correction formula.

Electrocardiogram parameter values are considered PCS if they meet or exceed the higher-limit PCS criteria listed in Table 6. The number and percentage of subjects with PCS post-baseline ECG values will be tabulated by treatment group for the double-blind treatment period. The percentages will be calculated relative to the number of subjects with non-PCS baseline values and at least 1 post-baseline assessment for the double-blind treatment period. The numerator is the total number of subjects with non-PCS baseline values and at least 1 PCS post-baseline value for the double-blind treatment period. A supportive tabular display of subjects with PCS post-baseline values will be provided, including the subject ID number, study center number, the baseline value, all post-baseline (including non-PCS) values, and change from baseline.

Table 6: Criteria for Potentially Clinically Significant (PCS) QTcB and QTcF

Parameter	Criteria
QTcB and QTcF	>450 to ≤480 msec
	>480 to ≤500 msec
	>500 msec
	Change from baseline >30 to ≤60 msec
	Change from baseline >60 msec

3.9.4. Abnormal Movement Scales

Extra pyramidal symptoms (EPS) will be evaluated as AEs and also as assessed by abnormal movement scales. Abnormal movement scales will include the following: Abnormal Involuntary Movement Scale (AIMS), Barnes Akathisia Rating Scale (BARS), and Simpson-Angus Scale (SAS).

For all abnormal movement scales, total scores and subscale scores will be summarized by treatment group at each visit for the absolute value and for changes from baseline.

Number and percentage of subjects meeting the criteria for treatment-emergent Parkinsonism (SAS total score >3), for treatment-emergent akathisia (BARS global clinical assessment of akathisia score ≥2), for treatment-emergent dyskinesia (AIMS score ≥3 on any of the first 7 items, or a score ≥2 on two or more of any of the first 7 items) at any post-baseline visit will be summarized by treatment group.

A listing will be provided for every abnormal movement scale. Listing for treatment-emergent EPS will be provided.

3.9.5. Columbia-Suicide Severity Rating Scale (C-SSRS)

The C-SSRS is a questionnaire used to measure the presence and intensity of suicidal ideation and behavior.

Suicidal behavior and suicidal ideation will be summarized descriptively. The number of subjects with suicidal ideation and suicidal behavior during the double-blind treatment period will be summarized by treatment group when applicable.

Supportive tabular display of subjects with all values will be provided, including subject ID number, treatment group, visit number, intensity of suicidal ideation, suicidal behavior type, and lethality of suicidal behavior.

Table 7: C-SSRS Categories for Analysis

Category	C-SSRS Item response is “YES”
Suicidal behavior	Preparatory acts or behavior Aborted attempt Interrupted attempt Actual attempt Complete suicide
Suicidal ideation	Wish to be dead Non-specific active suicidal thoughts Active suicidal ideation with any methods (not plan) without intent to act Active suicidal ideation with some intent to act, without specific plan Active suicidal ideation with specific plan and intent
Non-suicidal self-injurious behavior	Non-suicidal self-injurious behavior

3.10. Pharmacokinetic/ Pharmacodynamic Data Analysis

Subject listings for the PK sampling time and concentrations of olanzapine, samidorphan, and metabolites of interest will be provided. PK data obtained from plasma samples collected in this study may be included in a subsequent population PK analysis or other post-hoc analyses conducted outside the scope of this SAP.

4. INTERIM ANALYSIS

One unblinded interim analysis will be conducted by an independent statistical center (ISC) when 50% of subjects (N=200) have completed the double-blind treatment period or have discontinued from the study. The details regarding the conduct of the unblinded interim analysis will be specified in the [interim analysis operational plan](#) and the statistical testing methodology will be specified in the [interim analysis plan \(IAP\)](#).

The conditional power (CP) will be computed for both primary endpoints. Based on the conditional power, it will be assigned into one of 3 zones: favorable ($CP \geq 90\%$), promising ($30\% \leq CP < 90\%$), or unfavorable ($CP < 30\%$). The target sample size of 200 per arm will be increased to 270 subjects per arm when the conditional power for at least one primary endpoint is in the promising zone and neither of the primary endpoints are in the unfavorable zone. Otherwise, the target sample size will be maintained at 200 subjects per arm. Overall Type 1 error for the final analysis are maintained using CHW method (Cui et al, 1999) by combining the Z test statistics from two independent stages (before and after the interim analysis) with a fixed weight based on the original sample size. The weighted CHW statistics always controls type I error, as it does not depend on the design specifications, such as the sample size adaptation algorithm, the maximum

number to be increased, and the final sample size (Hung et al, 2014). There will be no early stopping for efficacy or futility. The sponsor will not be informed of any unblinded interim analysis results except for a recommendation to either increase the sample size to 540 subjects (270 per arm) or to leave the sample size unchanged.

5. CHANGES IN CONDUCT OR PLANNED ANALYSES FROM THE PROTOCOL

There are no major deviations from the protocol-specified analysis.

6. DEFINITIONS AND CONVENTIONS FOR HANDLING OF THE DATA

Dataset specifications will be provided in a separate document.

6.1. Analysis Visit Windows

Scheduled analysis visits are visits upon scheduled time points as specified in the protocol (Table 3 Schedule of Visits and Assessments).

Scheduled analysis visits during the study period will be the same as the nominal visits collected in the eCRF. There will be one valid value of assessment kept for each scheduled analysis visit in summary/ analysis statistics.

Unscheduled visits are visits with data collected outside of the scheduled time point. Unscheduled visits will not be used for by-visit summary/analysis statistics unless specified otherwise.

All unscheduled visit data as collected in eCRFs will be included in listings.

Visit Day is calculated as (visit date) – (date of the first dose of study drug) + 1.

Last post-baseline values are defined as the last valid post-baseline values collected for each subject during the double-blind treatment period.

Any post-baseline values are defined as any valid values collected from scheduled visits if applicable.

6.2. Handling of Partial Dates of Concomitant Medication

Partial start dates of prior and concomitant medications will be assumed to be the earliest possible date consistent with the partial date. Partial stop dates of prior and concomitant medications will be assumed to be the latest possible date consistent with the partial date. In the case of a completely missing stop date, medication will be assumed to be ongoing.

6.3. Handling of Safety Data

All efforts should be made to obtain any missing information from the investigator. For C-SSRS, vital signs, laboratory testing (chemistry, hematology, urinalysis), and 12-lead ECGs, only observed data will be used for analyses, and missing data will not be imputed.

7. GENERAL STATISTICAL METHODOLOGY

In general, summary statistics (n, mean, standard deviation [SD], median, minimum, and maximum for continuous variables, and number and percentage of subjects in each category for categorical variables) will be provided by treatment group. All summary tables will be based on observed data, and missing values will not be imputed unless otherwise indicated. Measurements collected from unscheduled visits or repeated assessments will not be included in the by-visit summary tables or figures, the analyses for the PCS post-baseline values, and subject listings. Source data for the summary tables and statistical analyses will be presented as subject data listings.

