3.9.2. Clinical Laboratory Parameters

Laboratory parameters will be presented in conventional (ie, US) units. Unless specified otherwise, only scheduled laboratory parameters will be included in the summaries. All laboratory data, including those collected at unscheduled visits, will be included in the listings.

Laboratory results (baseline and change from baseline) for the Safety Population during double-blind treatment period for chemistry and hematology parameters will be summarized by treatment group and by visit.

Number (percentage) of subjects with potentially clinically significant (PCS) values at any post-baseline visit, will be summarized by treatment group. PCS criteria are presented in [Table 1](#). The denominator is all subjects with non-PCS baseline and at least one post-baseline assessment in the Safety Population and the numerator is the number of subjects with non-PCS baseline and PCS at post-baseline. All PCS values including baseline PCS values will be included in supportive listings.

Shift tables for metabolic parameters (fasting glucose, total cholesterol, LDL, HDL, Triglycerides, and HbA1c) and liver function tests will be presented. The criteria are summarized in [Table 2](#), [Table 3](#) and [Table 4](#).

Table 1: Criteria of Potentially Clinically Significant (PCS) Abnormality for Selected Analytes

Parameters	Criteria
Chemistry	
Albumin	<2.5 g/dL
Alkaline Phosphatase (U/L)	$\geq 3 \times \text{ULN}$
Alanine Aminotransferase (U/L)	$\geq 3 \times \text{ULN}$
Aspartate Aminotransferase (U/L)	$\geq 3 \times \text{ULN}$
Bilirubin, Total	$\geq 2.0 \text{ mg/dL}$
Blood Urea Nitrogen	$> 30 \text{ mg/dL}$
Cholesterol, Random	$> 300 \text{ mg/dL}$
Cholesterol, Fasting	$\geq 240 \text{ mg/dL}$
Cholesterol, HDL Fasting	$\leq 30 \text{ mg/dL}$
Cholesterol, LDL Fasting	$\geq 160 \text{ mg/dL}$
Creatine Kinase (U/L)	$\geq 3 \times \text{ULN}$
Creatinine	$\geq 2.0 \text{ mg/dL}$
Glucose, Random	$< 50 \text{ mg/dL}$ or $\geq 200 \text{ mg/dL}$
Glucose, Fasting	$< 50 \text{ mg/dL}$ or $\geq 126 \text{ mg/dL}$
Potassium	$< 3 \text{ mmol/L}$ or $> 5.5 \text{ mmol/L}$
Lactate Dehydrogenase (U/L)	$> 3 \times \text{ULN}$
Prolactin (Female)	$> 30 \text{ ng/mL}$
Prolactin (Male)	$> 20 \text{ ng/mL}$
Sodium	$< 130 \text{ mmol/L}$ or $> 150 \text{ mmol/L}$
Triglycerides, Fasting (Female)	$\geq 120 \text{ mg/dL}$
Triglycerides, Fasting (Male)	$\geq 160 \text{ mg/dL}$

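### Laboratory PCS and shift tables described as covering any post-baseline visit leave out unscheduled and repeat values, so their subject counts can only be too low or unchanged

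*SAP*

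**What the plan says.** The scope is described broadly. SAP 3.9.2 plans to summarise the "Number (percentage) of subjects with potentially clinically significant (PCS) values at any post-baseline visit". Protocol 14.6 plans the same for laboratory, vital-sign, weight and ECG parameters. SAP Tables 2 to 4 are titled as shifts from baseline to any post-baseline value. For the PCS percentage, "The denominator is all subjects with non-PCS baseline and at least one post-baseline assessment in the Safety Population".

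Three SAP rules then narrow the data:

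- Section 7: measurements from "unscheduled visits or repeated assessments will not be included in the by-visit summary tables or figures, the analyses for the PCS post-baseline values". The same sentence leaves them out of subject listings.
- Section 3.9.2: unless specified otherwise, "only scheduled laboratory parameters will be included in the summaries". No exception is given for the PCS or shift tables.
- Section 6.1: "Any post-baseline values are defined as any valid values collected from scheduled visits if applicable". It also keeps one valid value per scheduled visit, and says that "Unscheduled visits are visits with data collected outside of the scheduled time point".

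On listings, two sections oppose Section 7. SAP 3.9.2 says "All laboratory data, including those collected at unscheduled visits, will be included in the listings", and SAP 6.1 says "All unscheduled visit data as collected in eCRFs will be included in listings".

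**The concern.** A table of subjects who ever crossed a threshold should use every valid value obtained. Under these rules, a laboratory value that meets a criterion only at an unscheduled draw or on a repeat is not counted. The plan itself provides for such values, because protocol 8.3.11.2 lets the investigator repeat laboratory assessments.

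Safety and tolerability is the secondary objective, and these are its threshold tables. Adverse event reporting does not fully close the gap. Under protocol 13.1 an out-of-range value becomes an adverse event only if the investigator judges it clinically significant, whereas PCS criteria are fixed cut-offs. Listings would be the other safeguard, but the SAP contradicts itself on them. SAP Section 5 reports no major deviation from the protocol's analyses, so the narrowing of protocol 14.6 is not acknowledged.

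**Working it through.** The documents give no figure to reproduce, because the point concerns which data enter the tables. The check sets the rules side by side, establishes the direction of the effect, and then looks at scale.

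**1. Which rule excludes what.** Section 7 names the PCS analyses, so it removes both unscheduled and repeat values from them. It does not name the shift tables. Unscheduled values leave those through 3.9.2 and 6.1, and repeats through the one-value-per-visit rule in 6.1.

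**2. Direction for counts.** Let S be a subject's scheduled post-baseline values and U the unscheduled and repeat ones. The subject is counted if at least one value meets the criterion. S is contained in S ∪ U, so adding U can turn a no into a yes but never the reverse. Baseline is fixed, since SAP 3.1 takes the last non-missing assessment before first dose without limiting it to scheduled visits. The scheduled-only count is therefore at most the full count. A simulation on invented values (3000 data sets of 60 subjects) agrees: adding the extra values raised the PCS count in 2989 data sets, left it unchanged in 11 and lowered it in 0.

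**3. Where the direction is not guaranteed.** The values below are invented to show the logic.

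- Percentages: 10/100 = 10.0% on scheduled values. If one more subject has only an unscheduled, non-PCS post-baseline value, using all values gives 10/101 = 9.9%. In the simulation the percentage fell in 104 data sets and rose in 2889.
- Bands, if assigned by worst value: HbA1c is 5.5 at baseline, 5.8 at a scheduled visit and 6.6 on repeat. Scheduled-only gives 1 in the row ≥5.7 and <6.5, and 0 in the row ≥6.5. All values give 0 and 1. The row ≥5.7 is 1 either way. The QTc bands in SAP Table 6 behave in the same way.

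**4. Scale, from protocol Table 3.** Visits 3 to 17 are 15 double-blind post-baseline visits.

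| Assessment | Scheduled weeks | Visits with | Visits without |
|---|---|---|---|
| Laboratory | 1, 2, 4, 8, 12, 16, 20, 24 | 8 | 15 − 8 = 7 |
| AIMS, BARS, SAS | 4, 12, 24 | 3 | 15 − 3 = 12 |

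These are opportunities for unscheduled values, not numbers of values lost. With an unchanged denominator no larger than the arm, one missed subject lowers the percentage by at least 1/200 = 0.50 points, or 1/270 = 0.37 points. SAP Table 8 reports percentages to one decimal place, so such a change would show.

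**5. Movement scales.** Protocol 8.3.9.3.1 calls for an unscheduled assessment when a subject complains of extrapyramidal symptoms on a day without scheduled scales. Section 7 does not name these thresholds, so they drop out only through 6.1. That section does not settle whether a complaint-triggered scale at, say, Week 5 counts as collected at a scheduled visit. Exclusion is possible here but not certain.

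**6. A separate point in the opposite direction.** SAP 3.9.4 calls its parkinsonism, akathisia and dyskinesia thresholds treatment-emergent but states no baseline condition. The laboratory rule (3.9.2) and the ECG rule (3.9.3.2) both require a non-PCS baseline. As written, a subject who already met a movement criterion at baseline could be counted, so these counts could be too high.

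**The case against.** The strongest reply is that scheduled-only counting is a pre-specified choice. Sections 3.9.2, 6.1 and 7 agree on it for the PCS tables, any post-baseline visit can be read as any visit in Table 3, and both arms then get the same planned assessments. Using all values makes the counts depend partly on how often extra tests are ordered. That cost is real, but it is met by showing the scheduled-only count alongside. It does not explain why a table described as covering any post-baseline visit, and so specified in the protocol, should omit a valid value that crosses the threshold.

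Several limits stand:

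- A repeat of a scheduled test presupposes a scheduled value. If that value met the criterion and was kept, nothing is lost. A loss needs a non-qualifying original with a qualifying repeat, or a draw off schedule.
- Subjects who withdraw are asked to attend an early termination visit that includes laboratory tests, which may supply another scheduled value.
- Complaint-triggered movement symptoms should also be recorded as adverse events, and SAP 3.9.1.1 summarises these.
- No specific source of unscheduled ECG or vital-sign values is documented.
- The listings conflict is a matter of one clause, although it needs correcting whichever counting rule is kept.

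**Conclusion.** The concern holds. Under the SAP as written, subject counts for laboratory PCS and shift criteria can only be too low or unchanged relative to the any-post-baseline scope that the documents describe. This assumes that baseline is fixed, that any qualifying value counts, and that repeats add to the data rather than replace values judged invalid. It does not extend strictly to percentages or to bands assigned by worst value. The number of subjects affected and the effect on the comparison of arms cannot be derived, because the documents give no frequency of unscheduled or repeat tests; both could be zero. The consequence is confined to descriptive safety tables. Adverse event incidence and the primary and key secondary endpoints are untouched. The SAP should be changed, but the validity of the trial does not turn on it. Confidence is high for the laboratory rules and lower for the movement scales.

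**What to change.** In SAP 3.9.2, 6.1 and 7:

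- Base PCS, shift and movement-scale counts described as any post-baseline on all valid double-blind post-baseline values: scheduled, unscheduled and repeat. Do the same for orthostatic and QTc counts where such values exist.
- Replace the qualifier about applicability in 6.1 with this rule, and say that the one-value-per-visit rule governs by-visit summaries only.
- Keep by-visit summaries on scheduled values, and give the scheduled-only threshold counts as a supportive table.
- State whether the HbA1c and QTc bands are assigned by worst value.
- Remove subject listings from the exclusion in Section 7, so that it agrees with 3.9.2 and 6.1.

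Separately, in SAP 3.9.4, count a movement criterion as treatment-emergent only if it was not met at baseline.

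The cost is SAP wording and one supportive table. No new data are needed: unscheduled data are already planned for listings under 3.9.2 and 6.1, and protocol 18.1 sends central laboratory data directly to the sponsor for the final datasets. The drawback is that counts will partly reflect how often extra assessments are ordered, which the supportive table makes visible.

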7.1. Reporting Precision

Summary statistics will be presented to the following degree of precision, unless otherwise specified:

Table 8: Degree of Precision

Statistics	Degree of Precision
Mean, Median, Confidence limit boundaries	One more than the raw data, up to 3 decimal places
Standard deviation, Standard error	One more than the mean, up to 3 decimal places
Minimum, Maximum	The same as the raw data, up to 2 decimal places
p-value	Rounded to 3 decimal places and therefore presented as 0.xxx; p-values smaller than 0.001 as '<0.001'; p-values greater than 0.999 as '>0.999'
Percentage	One decimal place. A percentage of 100% will be reported as 100%. Percentages of zero will be reported as 0

Fractional numeric values will be presented with a zero to the left of the decimal point (for example, 0.12 – 0.30).

For weight, height, and BMI, one decimal place will be used for summary statistics.

8. PROGRAMMING SPECIFICATIONS

Programming specifications will be provided in a separate document.

9. MOCK TABLES, LISTINGS AND GRAPHS (TLGS)

Mock-up tables and listings will be provided in a separate document.

